PROTOCOL TITLE: Targeted Neuroplasticity after Spinal Cord Injury**PRINCIPAL INVESTIGATOR:**

[name]

Neuromodulation Lab
 Shirley Ryan AbilityLab (22nd floor)
 [name]
 [name]

Site(s) where study will be performed:

Version Date	8/5/2021
Investigational Agent(s) (Drugs or Devices)	
IND / IDE / HDE #	
Indicate Special Population(s)	 Children  Children who are wards of the state  Adults Unable to Consent  Cognitively Impaired Adults  Neonates of Uncertain Viability  Pregnant Women  Prisoners (or other detained/paroled individuals)  Students/Employees N/A
Sample Size	500
Funding Source	Institutional funds/Northwestern University
Indicate the type of consent to be obtained	 Written  Verbal/Waiver of Documentation of Informed Consent  Waiver of HIPAA Authorization  Waiver/Alteration of Consent Process
Site	 Lead Site (For A Multiple Site Research Study)  Data Coordinating Center (DCC)
Research Related Radiation Exposure	 Yes  No
DSMB / DMC / IDMC	 Yes  No

OBJECTIVES:

The purpose of this study is to test a strategy to restore upper and lower-limb motor function in individuals with spinal cord injury (SCI). We have the following two specific aims:

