Aim 1. Maximize exercise-mediated recovery of limb muscles by using stimulation induced spinal plasticity. We will study the effect of limb training combined with Spike-Timing Dependent Plasticity (STDP) on motor function recovery. We will test the effect of three groups: (1) stimulation, (2) training +stimulation, and (3) training+sham stimulation. We hypothesize that the ability of training to promote recovery of limb motor function will be enhanced by eliciting STDP in upper and lower-limb. An important strength of this aim is the combination of training and STDP, which aims at enhancing the beneficial effects of motor training by promoting plasticity in the corticospinal pathway (Ellaway et al., 2007; Castel et al., 2009). Training effects on physiological pathways will be explored and correlated with hand/arm motor function and the site and extent of the lesion defined by structural MRI.

Aim 2. Maximize exercise-mediated recovery of limb muscles by using stimulation induced spinal plasticity. STDP has been shown to be effective in enhancing the recovery of residual limb function in humans with chronic incomplete SCI (Urbin et al., 2017). In this aim we will investigate the effect of the combination of extended STDP and training. We hypothesize the ability of training to promote recovery of motor function will be enhanced by eliciting STDP in the corticospinal pathway.

BACKGROUND:

After a SCI, many individuals present deficits in upper-limb and/or lower-limb function. Most SCIs are contusions and ~50% occur at the cervical level causing anatomically incomplete damage and bilaterally functional deficits to lower- and upper-limbs (Kakulas, 1999). Arm and leg function deficits limit daily-life activities, such as reaching and grasping, eating, writing, and walking which decreases the quality of life (Snoek et al., 2004). Regaining arm and leg function is considered the highest priority for improving the quality of life of individuals with SCI (Anderson, 2004).

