TMS and PNS/spinal root interstimulus interval (ISI). The ISI between TMS and PNS/spinal root stimulation will be set to allow descending volleys elicited by TMS to arrive at the presynaptic terminal of corticospinal neurons ~1-2 ms before antidromic PNS/spinal root volleys reach the motoneurons reach during STDP. The methods for timing the arrival of volleys at the spinal cord have been described previously (Bunday and Perez, 2012; Urbin et al., 2017; Bunday et al., 2018). Briefly, the ISI will be tailored to individual subjects based on conduction times calculated from latencies of MEPs, F-wave, and M-max. MEP latencies will be recorded during isometric ~10% of MVC of the target muscle to determine the shortest and clearest response for our estimations. The onset latency will be defined as the time when each response exceeds 2 SD of the mean rectified pre-stimulus activity (100 ms) in the averaged waveform. Peripheral conduction time (PCT) will be calculated using the following equation:

$$\text{PCT} = (\text{F-wave latency} - \text{M-max latency}) \times 0.5$$

Central conduction time (CTT) will be calculated using the following equation:

$$\text{CCT} = \text{MEP latency} - (\text{PCT} + \text{M-max latency})$$

Upper limb training

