If eligible, participants will be asked to complete pre, post, and follow-up assessment sessions in addition to the training sessions. Each assessment will require 2-5 sessions. Participants will complete up to 135 training sessions with a maximum of 360 paired pulses of stimulation and a small cohort of participants (n=10) will complete up to 270 training sessions with a maximum of 720 paired pulse of stimulation (up to 4 times per day). This will be determined based on preliminary data. In Aim 1, participants will be tested before and after at least 10 training sessions with single site stimulation. In Aim 2, participants will be tested before and after at least 40 training sessions with multisite stimulation. If a training session is not completed or missed participants will be asked to recover that session in a timely manner.

AIM 1: Randomized controlled design

Pre-assessment: 1. Physiology 2. Kinematics 3. Function	Stimulation Training + stimulation Training + sham stimulation	Post-assessment: 1. Physiology 2. Kinematics 3. Function	Follow-up assessment: 1. Physiology 2. Kinematics 3. Function
--	--	---	--

AIM 2:

Pre-assessment: 1. Physiology 2. Kinematics 3. Function	Training + stimulation	Post-assessment: 1. Physiology 2. Kinematics 3. Function	Follow-up assessment: 1. Physiology 2. Kinematics 3. Function
--	------------------------	---	--

We anticipate that each participant will take about 2-10 months to complete the study procedures/testing. Follow-up assessments will be done 1-9 months after completion of protocol, one follow-up in the first 3 months and the last follow-up in the 4-9 months following the last completed session. We will evaluate the subject's ability to move their hands, arms, legs, feet and/or toes using the different physiological and functional tests as mentioned above. TMS measurements, CMEPS and EMG recordings may also be done at these follow-up assessments.

INCLUSION AND EXCLUSION CRITERIA:

We anticipate the screening of 500 subjects across the two aims (60 subjects for Aim 1, and 40 for Aim 2) who have incomplete SCI at the cervical/thoracic/lumbar level (C2-L2). This number accounts for an attrition rate of 50%. To account for screen failures we would like to ask for a total of 200 subjects.

- Inclusion criteria for SCI subjects:
 - (1) Male and females between ages 18-85 years
 - (2) SCI at least 4 weeks post injury
 - (3) Spinal Cord injury at or above L2
 - (4) ASIA A,B,C, or D, complete or incomplete

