 - (5) Possess the following abilities
 - (Aim 1) The ability to produce a visible precision grip force with one hand, and/or the ability to perform some small wrist flexion and extension (Aim 2) The ability to perform a small visible contraction with dorsiflexion and hip flexor muscles

- Exclusion criteria for SCI Subjects:
 - (1) Uncontrolled medical problems including pulmonary, cardiovascular or orthopedic disease
 - (2) Any debilitating disease prior to the SCI that caused exercise intolerance
 - (3) Premorbid, ongoing major depression or psychosis, altered cognitive status
 - (4) History of head injury or stroke
 - (5) Vascular, traumatic, tumoral, infectious, or metabolic lesion of the brain, even without history of seizure, and without anticonvulsant medication
 - (6) History of seizures or epilepsy
 - (7) Receiving drugs acting primarily on the central nervous system, which lower the seizure threshold (see appendix 2)
 - (8) Pregnant females
 - (9) Ongoing cord compression or a syrinx in the spinal cord or who suffer from a spinal cord disease such as spinal stenosis, spina bifida, MS, or herniated disk
 - (10) Metal plate in skull
 - (11) Individuals with scalp shrapnel, cochlear implants, or aneurysm clips

RECRUITMENT METHODS:

We anticipate screening of 500 subjects to complete the study (see description above). We will be using the IRB approved SCI registry for recruitment. A letter granting access to the registry is included in the submission. Subjects who have previously expressed an interest in participating in research studies at the Shirley Ryan AbilityLab complete a questionnaire and request that their information be entered into the research volunteer database. This database is searchable based on criteria such as age, time-post injury and injury level. Potential subjects will be called by the study coordinator. If the individuals have not agreed to be contacted by phone for future studies then the treating physician will be the one contacting them. The phone call will be to provide information about the study to the individual to determine if they are interested in the study. We will not be collecting any information from the individual. All the screening will be done after written consent is collected and before enrollment.

COMPENSATION FOR PARTICIPATION IN RESEARCH ACTIVITIES:

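### The eligibility section calls the population incomplete SCI and then admits complete injuries, so the plan does not fix whom it enrols or whom its result covers

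*Combined protocol and SAP*

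**What the plan says.** All references are to the combined protocol and SAP.

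**Population.** The lead-in to the inclusion and exclusion criteria forecasts screening for both aims and describes the subjects as people "who have incomplete SCI at the cervical/thoracic/lumbar level (C2-L2". The numbered list that follows has three relevant entries:

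- Criterion 3 restricts level only: "Spinal Cord injury at or above L2".
- Criterion 4 restricts nothing by completeness: "ASIA A,B,C, or D, complete or incomplete".
- Criterion 5 asks for residual movement. For Aim 1 it is "The ability to produce a visible precision grip force with one hand, and/or the ability to perform some small wrist flexion and extension". For Aim 2 it is "The ability to perform a small visible contraction with dorsiflexion and hip flexor muscles".

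The exclusion list has no completeness rule. The Objectives say only that the strategy is to "restore upper and lower-limb motor function in individuals with spinal cord injury (SCI". The Aim 2 rationale cites evidence that the method was "effective in enhancing the recovery of residual limb function in humans with chronic incomplete SCI".

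**Analysis.** Under Statistical Analysis, Aim 1 is a repeated-measures ANOVA with Tukey comparisons, with factors GROUP and TIME, on 45 participants (15 per group) at alpha 0.05 and power 0.8. There is no stratum, covariate or subgroup for completeness. No effect size or SD is given.

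**Timing of stimulation.** In the subsection on the interstimulus interval (ISI), "the ISI will be tailored to individual subjects based on conduction times calculated from latencies of MEPs, F-wave, and M-max". Central conduction time is obtained by subtraction from the MEP latency.

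**The concern.** Two sentences in one section define two different populations. Screening staff could apply either, and a report could describe either. With 15 per arm and no completeness term in the analysis, a chance imbalance between arms in complete injuries would also go unadjusted.

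The delivery of the intervention raises a second, related question. The ISI depends on an MEP latency, yet none of the entry criteria refers to an MEP. A participant without one in the muscle to be stimulated would have no interval calculable by the stated method. If such participants were enrolled and did not respond, they would dilute the comparison of training+stimulation with training+sham.

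**Working it through.** **Step 1. Can any other text decide between the two statements?** Criterion 3, the Objectives and the exclusion list are silent on completeness. The Aim 2 rationale describes earlier evidence, not an entry rule. That leaves criterion 5.

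**Step 2. Test criterion 5 with a case.** Take a person whose injury is complete but lies below the segments that serve the hand and wrist.

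| Text | Aim 1 result |
|---|---|
| Criterion 3 (at or above L2) | met |
| Criterion 4 (A to D, complete or incomplete) | met |
| Criterion 5, Aim 1 (grip and/or wrist movement) | met |
| Lead-in (incomplete SCI) | not met |

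The same person is inside the list and outside the lead-in. For Aim 2, criterion 5 requires visible leg contraction and narrows entry much more. If it removed every complete injury, criterion 4 would be wrong as written for that aim; if it does not, the conflict remains there too. In either case a sentence needs correcting.

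The gap is widest in Aim 1 because its objective covers upper and lower limb, and the Study Endpoints use the 10-meter walk for those doing lower-limb exercise, while the ability rule concerns only hand and wrist.

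**Step 3. What the ISI needs.** The stated formulas are:

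- PCT = (F-wave latency − M-max latency) × 0.5
- CCT = MEP latency − (PCT + M-max latency)

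Without an MEP latency, CCT is undefined. The ISI subsection offers no substitute. The muscles listed for stimulation include tibialis anterior and soleus, which the Aim 1 ability rule does not touch. None of this depends on the completeness grade.

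**Step 4. Illustration of dilution.** The plan's 15 per group cannot be reproduced, because no effect size is stated. Working backwards, assuming a two-sided alpha of 0.05 and an unadjusted two-sample t-test:

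- df = 2 × 15 − 2 = 28; critical t = 2.048
- noncentrality = d × √(15/2)
- 80% power requires d = 1.06 (noncentrality 2.90)

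If a share p of participants has no effect and the SD is unchanged, the effect becomes d × (1 − p):

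| Assumed p | d × (1 − p) | Noncentrality | Power |
|---|---|---|---|
| 0 | 1.06 | 2.90 | 80% |
| 5% | 1.01 | 2.76 | 76% |
| 10% | 0.95 | 2.61 | 71% |
| 20% | 0.85 | 2.32 | 61% |
| 33% | 0.71 | 1.94 | 47% |

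A Tukey-adjusted comparison of the three arms at one time point (critical value 2.43 on 42 df) needs d = 1.20 for 80% power. Scaled the same way, it gives about 75%, 70%, 58% and 42%. The scaling applies to training+stimulation versus training+sham. It does not carry over to stimulation versus training+stimulation, where both arms are stimulated.

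**The case against.** **The list governs.** The word incomplete sits in a screening forecast, whereas the numbered list is explicit and names all four grades. The natural reading is that the list is operative and the lead-in was not updated. That is fair, and it makes this a wording correction. But the document does not say so, and the wording in question decides who is enrolled.

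**Lesion severity is not ignored.** Aim 1 plans to correlate training effects on physiological pathways with the site and extent of the lesion on MRI. This is exploratory and does not adjust the group comparison.

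**A complete injury means no interval.** A reader might infer that admitting complete injuries makes the intervention undeliverable. The documents do not support this. They nowhere equate a complete grade with an absent MEP. Someone graded complete who meets criterion 5 has voluntary output in the tested limb, and someone graded incomplete could lack an MEP in a given muscle. The MEP item under Study Endpoints directs TMS in people with SCI to a muscle that still has a connection, and the TMS subsection locates the coil by the largest MEP, so the procedure presupposes one. What remains is that none of this is an entry rule.

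**Power falls to 61% or 47%.** A reader might take these as the expected cost. They are not plan figures: d is back-solved, the shares are assumptions without a source in the documents, and the test is simpler than the one planned. At a share of 5% the loss is about four points.

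**A baseline MEP should be mandatory because it is already recorded.** This is not established. The secondary measurements, MEPs among them, are ones that participants may complete, and nothing says that an ISI is set for sham participants. An MEP entry rule could add a procedure before randomisation, and reconciling the completeness wording does not require it.

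**Conclusion.** The contradiction is certain and rests on the text alone: the lead-in and criterion 4 cannot both describe the population, and criterion 5 does not decide between them. It should be corrected, because it determines who enters and to whom the result applies. How many participants it affects is unknown, since the plan gives no expected share of complete injuries.

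The missing link between eligibility and the MEP-based interval is a separate and narrower gap. It holds at every completeness grade, and earlier text on muscle selection partly covers it. The power figures show direction only. They rest on the back-solved effect, complete non-response in the assumed share, an unchanged SD and the single contrast with sham. Which population is appropriate is for the sponsor.

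**What to change.** 1. Rewrite the lead-in and criterion 4 so that they name one population, and report results for that population. This costs only wording.
2. If complete injuries remain eligible, add complete versus incomplete as a covariate in the Aim 1 analysis. The ASIA grade is already needed for criterion 4, so no new data are required. The term should apply to change over time and not only to overall level. For a single pre-to-post change with 45 participants in three groups, it costs one degree of freedom: error df go from 45 − 3 = 42 to 41.
3. Separately, reconcile the eligibility criteria with the ISI calculation for the muscle to be stimulated, and say what happens when no MEP latency can be obtained. The choice of rule is the sponsor's. If the choice is a baseline MEP requirement, the cost is a TMS test before randomisation in all arms and the loss of those without a response.
4. Any statement about power loss should be labelled hypothetical until an effect size and an expected share without an MEP are given.

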Please be advised: Inactivity on the card for more than 3 months will incur a monthly fee. However, as long as there is activity on the card within 3 months (funds are added or a transaction is completed), the month period will reset and no monthly fee will be assessed. If the participant do incur a monthly fee, please contact Greenphire Support at the number on the back of the card and they will reverse the fee. See "Tips for Using the Attached ClinCard" for more information. The Finance Department at the Rehabilitation Institute of Chicago will be provided with the participant's information, including their Social Security Number, in order to issue payment for the study participation. Study payments are considered taxable income and reportable to the Internal Revenue Service (IRS). An IRS Form 1099 will be sent to the participant if the total payments are \$600 or more in a calendar year.

The participant may be given access to new inventions that are being developed by the investigator, the study sponsor, or other people involved in the study. Certain laws can make it harder to obtain legal protection for a new invention shared with a study participant, unless the study participant agrees to keep information about the invention confidential. The participant agree to keep confidential information they may receive about new inventions, such as new drugs, new devices, or new methods.

WITHDRAWAL OF PARTICIPANTS:

Subjects will be allowed to withdraw from the study at any time upon request. Their participation will be terminated if any of the inclusion criteria ceases to be valid or if any exclusion criteria will manifest after enrollment. Occurrence or participant reporting of any of the following during the course of the study may lead to withdrawal by study team:

- Change in dosage for neuro-active medications (Baclofen, Lyrica, Celebrex, Cymbalta, Gabapentin, Naprosyn, Diclofenac, Diazepam, Tramadol, etc.) within 2 weeks of any study visit.
- Skull fractures, skull deficits or concussion within the last 6 months
- Unexplained recurring headaches
- Sleep deprivation, alcoholism
- Claustrophobia precluding MRI
- Pregnancy

RISKS TO PARTICIPANTS:

Muscle Activity Recording (EMG): Mild discomfort, such as tingling, an itching sensation may be felt under the electrodes that register the response in the participants muscles. We will clean the area with alcohol and use standard, hospital grade electrodes.

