Spinal stability for inpatient subjects with cervical injuries: TMS over the primary motor cortex and cervical roots and also electrical stimulation applied over the brachial plexus and the spinal cord can generate neck muscle contractions and head movement. Therefore, testing will be conducted using head and neck support. We will use the patient's own cervical-collar/neck brace during

testing. In the event a patient is not using a cervical collar/neck brace, we will provide a neck brace for use during testing. In addition, to ensure that there are no concerns about spine stability, prior to enrolling a patient with any injury level, we will get a written authorization from the patient's neurosurgeon and/or SCI care physician at the SRALab approving the patients' participation in all study procedures.

Subjects Screening: Individuals with brain and spinal cord injury are commonly recruited for noninvasive brain stimulation studies, and providing they have no history of seizure disorder and do not meet any of the other exclusion criteria as determined by the TMS safety check (separate file uploaded in the documents list), they are a clinical population to which TMS can be safely applied. All individuals will be carefully screened for the following contraindications to TMS (as listed in the protocol, consent form, and separate TMS safety checklist): pacemakers, metal implants in the head region, history of epilepsy or seizures, skull fractures or skull deficits, concussion within the last 6 months, unexplained recurring headaches, medications that lower seizure threshold, and pregnancy), changes in neuro-active medication dosing within 2 weeks of baseline assessments and across the duration of the study. Individuals with any such contraindications will be excluded from the study. Therefore those individuals included will only be those to which TMS can be safely applied. A majority of the studies conducted by our collaborators over the last 10 years have included patients with brain and/or spinal cord injury, and no reportable adverse events have occurred during TMS interventions similar to this proposal.

Statistical Analysis:

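### Pregnancy on study falls under both a mandatory and a discretionary withdrawal rule, the mandatory rule gives up outcomes that need no TMS, and the dose-change rules differ (minor)

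*Combined protocol and SAP*

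**What the plan says.** The Withdrawal of Participants section gives two rules in consecutive sentences. The first is mandatory: "Their participation will be terminated if any of the inclusion criteria ceases to be valid or if any exclusion criteria will manifest after enrollment". The second is discretionary: "Occurrence or participant reporting of any of the following during the course of the study may lead to withdrawal by study team". Six bullets follow the second. The first bullet is a change in the dose of a neuro-active medication "within 2 weeks of any study visit"; the last is pregnancy.

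The exclusion list in Inclusion and Exclusion Criteria has eleven items and includes "8) Pregnant females". Dose changes are not on it.

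Under Risks to Participants, the Subjects Screening paragraph lists contraindications to TMS. They include pregnancy and "changes in neuro-active medication dosing within 2 weeks of baseline assessments and across the duration of the study". The consequence is stated as "Individuals with any such contraindications will be excluded from the study".

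Three other places bear on the point:

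- Study Endpoints names GRASSP and the 10-meter walk as the primary outcomes. Neither uses TMS.
- Study Timeline allows TMS measurements and CMEPs to be repeated at follow-up.
- Statistical Analysis plans 15 participants in each of three Aim 1 groups, analysed by repeated-measures ANOVA. It does not say how participants withdrawn after randomization are handled.

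**The concern.** A coordinator who learns that a participant is pregnant finds one sentence that ends participation and a second that hands the decision to the study team. No text says which prevails. The protocol's cover table marks no data monitoring committee, so the discretion would rest with the study team alone. Whether to go on stimulating a pregnant participant should not depend on which sentence is read.

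The mandatory sentence has a statistical cost of its own. It ends participation, not just stimulation, and so read literally it ends outcome collection for someone already randomized. Neither rule describes the middle course of stopping the intervention and still measuring the primary outcome.

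For neuro-active dose changes, two sections attach different consequences and different time windows to the same event.

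**Working it through.** No figure in the plan depends on this wording, so the main check is a comparison of the rules.

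**1. Rules side by side**

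| Event after enrollment | Withdrawal section, first sentence | Withdrawal section, list | Subjects Screening |
|---|---|---|---|
| Pregnancy | Covered through exclusion 8: termination | Discretionary | Contraindication: excluded |
| Neuro-active dose change | Not covered (not an exclusion criterion) | Discretionary, within 2 weeks of a visit | Contraindication at baseline and throughout the study: excluded |

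For pregnancy, two of three entries are mandatory and one is discretionary. If the mandatory sentence governs, the pregnancy bullet has no function. For dose changes, the first sentence does not settle the matter, because the event is absent from the exclusion list.

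**2. What a lost outcome is worth in Aim 1**

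Input: 15 per group (Statistical Analysis). One participant is 1/15 = 6.7% of an arm. In its usual complete-case form, repeated-measures ANOVA would also drop that participant's earlier data.

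**3. How far the dose-change windows differ**

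Assumptions: training sessions count as study visits, and the two weeks run on either side of a visit. Lower Limb Training expects at least 3 sessions a week; I assume the same for the upper limb.

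- Two consecutive visits leave a day uncovered only if they are more than 14 + 14 = 28 days apart.
- At 3 sessions a week the spacing is about 7/3 = 2.3 days. No training day is uncovered, so during training only the consequence differs (may versus will).
- Aim 1 follow-ups are planned around 3 and 6 months. A three-month gap is about 365/4 = 91 days, which leaves about 91 − 28 = 63 days outside the withdrawal section's window but inside the Subjects Screening rule. No training stimulation is given then.

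**4. Frequency**

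The documents give no rate for pregnancy or for dose changes, so an expected number of affected participants cannot be calculated.

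**The case against.** The strongest reply is that the two pregnancy sentences can both be obeyed. Terminating a pregnant participant satisfies the mandatory rule and is also permitted by the discretionary one. That is right, and it is why this is an ambiguity to remove and not a flat contradiction. A reader might infer that the protocol authorizes stimulation in pregnancy. It does not: the mandatory sentence and the Subjects Screening list both point the other way.

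A second reply is that ending participation is a legitimate conservative choice and that pregnancy is not only a TMS matter. The study also uses CMEPs, spinal stimulation, 3 Tesla MRI and a startling sound above 115 dB, and the 10-meter walk may be done with body-weight support. This stands as far as it goes. Stopping TMS alone would be too narrow, and retention has to depend on medical safety. It does not justify giving up GRASSP or a timed walk in a participant who can do them safely and agrees to.

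A third reply is that Subjects Screening describes entry. That weakens any wider claim. A reader might extend the conflict to "Skull fractures, skull deficits or concussion within the last 6 months" and to unexplained recurring headaches, which appear in both places. Those items carry no on-study wording in the screening paragraph, so the overlap exists only if that list also counts as exclusion criteria after enrollment. Concussion might also be brought under "4) History of head injury or stroke", but that is interpretation. The dose-change clause is different: its reference to the whole study can only apply after enrollment.

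Finally, the triggers that force termination should be rare, and the plan already allows for 50% attrition. That is a fair reason to keep the point minor.

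**Conclusion.** The point holds as a minor, inexpensive improvement with three parts:

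- Pregnancy after enrollment is under a mandatory and a discretionary rule. The mandatory one probably governs, but the text does not say so.
- The mandatory rule, followed literally, discards primary outcomes after randomization. Each loss is 6.7% of a 15-person Aim 1 group.
- The dose-change rules differ in consequence during training, and in both consequence and window between follow-up visits.

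No sample-size or power figure changes. A reader might infer that a whole course of stimulation is at stake, or that discretionary withdrawal has biased the group comparison. The documents support neither: no trigger rate is given, and nothing shows that the discretion has been used unevenly. The verdict assumes that ending participation includes ending assessments, which is the literal sense of the sentence, and that training sessions count as study visits.

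**What to change.** 1. In Withdrawal of Participants, delete pregnancy from the discretionary list.

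2. Amend the termination sentence for exclusion criteria that appear after enrollment. Suggested text:

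> If an exclusion criterion appears after enrollment, stimulation (active or sham) and every procedure contraindicated by that criterion stop, including at follow-up: TMS measures and, for pregnancy, also CMEPs, spinal stimulation, MRI and startle testing. Participants who agree, and for whom it is medically safe, remain for the scheduled GRASSP or 10-meter walk assessments and, in Aim 1, are analysed in their randomized group.

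The sponsor should confirm which procedures each criterion rules out, and whether exercise training continues. The clause on lapsed inclusion criteria and the exclusion list itself can stay as they are.

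3. As a secondary alignment, limit the dose-change clause in Subjects Screening to the two weeks before baseline, and let the withdrawal section's rule govern on study.

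Cost: wording changes in two sections and no new visit types. Some participants who would have been terminated will attend visits already in the schedule. At most this is the post-assessment and two follow-ups, at 2-5 sessions each and $30 a session: 3 × 2 × $30 = $180 to 3 × 5 × $30 = $450 per retained participant, before any payment for extra hours. It would be less if only the primary outcome is measured. The study team also loses discretion to continue stimulation in pregnancy.
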